### CHAPTER III Theoretical Framework, Conceptual Framework, and Operational Definitions

**Image 1. Theoretical Framework**

**Image 2. Conceptual Framework**

**Table 1. Operational Definitions**

Variable	Definition	Scale	Measurement Criteria
Age	Age <12 months	Patient age categorized as less than 12 months.	Categorical
	Age >12 months	Patient age categorized as more than 12 months.	Categorical
Weight	Weight	Patient weight measured using a scale before intervention.	Numeric
RACHS	RACHS	Risk stratification for cardiac surgery.	Categorical Ordinal
Operation Type	Off CPB	Surgery without the use of cardiopulmonary bypass.	Categorical
	CPB	Surgery without the use of cardiopulmonary bypass.	Categorical
Gender	Male	Male patient.	Categorical
	Female	Female patient.	Categorical
Malnutrition	Yes	Patient diagnosed with malnutrition based on clinical assessment.	Categorical
	No	Patient not diagnosed with malnutrition based on clinical assessment.	Categorical
Respiration Diagnosis at Extubation	Pneumonia	Patient diagnosed with pneumonia at the time of extubation.	Categorical
	Effusion	Patient diagnosed with pleural effusion at the time of extubation.	Categorical

Vasoactive-Inotropic Score before Extubation	VIS	Vasoactive-Inotropic Score (VIS) to assess inotropic and vasoconstrictor therapy before extubation.	Numeric	VIS based on Drug Dosage	Calculation on Drug Dosage
ABG 1 hour before extubation	pH	Arterial blood pH measured 1 hour before extubation.	Numeric	Arterial Blood Gas (ABG) Measurement	
	PCO2	Partial pressure of carbon dioxide (PaCO2) in blood, measured 1 hour before extubation	Numeric	Arterial Blood Gas (ABG) Measurement	
	PaO2	Partial pressure of oxygen (PaO2) in blood, measured 1 hour before extubation	Numeric	Arterial Blood Gas (ABG) Measurement	
	BE (Base Excess)	Base excess or deficit in blood, measured 1 hour before extubation	Numeric	Arterial Blood Gas (ABG) Measurement	
	HCO3	Bicarbonate concentration in blood, measured 1 hour before extubation	Numeric	Arterial Blood Gas (ABG) Measurement	
	PF ratio	Ratio of PaO2 to FiO2, measured 1 hour before extubation	Numeric	Arterial Blood Gas (ABG) Measurement	
	OI/OSI	Oxygenation Index (OI) or Oxygen Saturation Index (OSI), measured 1 hour before extubation	Numeric	Arterial Blood Gas (ABG) Measurement	
Weaning Method	Pressure Support	Ventilator weaning method with pressure support.	Categorical	Medical Records on the Method Used	
	T-piece	Ventilator weaning method using a T-Piece without pressure support.	Categorical	Medical Records on the Method Used	
ABG 1 hour after NIV/HFNC	pH	Arterial blood pH measured 1 hour after initiation of NIV or HFNC.	Numeric	Arterial Blood Gas (ABG) Measurement	
	PCO2	Partial pressure of carbon dioxide (PaCO2) in blood, measured 1 hour after initiation of NIV or HFNC	Numeric	Arterial Blood Gas (ABG) Measurement	
	PaO2	Partial pressure of oxygen (PaO2) in blood, measured 1 hour after initiation of NIV or HFNC	Numeric	Arterial Blood Gas (ABG) Measurement	
	BE (Base Excess)	Base excess or deficit in blood, measured 1 hour after initiation of NIV or HFNC	Numeric	Arterial Blood Gas (ABG) Measurement	
	HCO3	Bicarbonate concentration in blood, measured 1 hour after initiation of NIV or HFNC	Numeric	Arterial Blood Gas (ABG) Measurement	
	PF ratio	Ratio of PaO2 to FiO2, measured 1 hour after initiation of NIV or HFNC	Numeric	Arterial Blood Gas (ABG) Measurement	
	OI/OSI	Oxygenation Index (OI) or Oxygen Saturation Index (OSI), measured 1 hour after initiation of NIV or HFNC	Numeric	Arterial Blood Gas (ABG) Measurement	
Successful Extubation	No Reintubation in 72 hours	Patient does not require reintubation within 72 hours after extubation	Categorical	Based on Clinical Observation	
Extubation Failure	Reintubation within 72 hours	Patient requires reintubation within 72 hours after extubation	Categorical	Based on Clinical Observation	
Reintubation	Reintubasi at 72 hours, 7 days and 28 Days	Frequency of patients requiring reintubation at 72 hours, 7 days and 28 days	Categorical	Based on Clinical Observation	
Mortality in CICU	Mortality During CICU Stay	Number of patient deaths during CICU hospitalization	Categorical	Based on Mortality Records	
Length of CICU Stay	Total Length of CICU Stay (in Days)	Total length of CICU stay measured in days	Numeric	Based on Hospital Records	
Length of Hospital Stay	Total Length of Hospital Stay (in Days)	Total length of hospital stay measured in days	Numeric	Based on Hospital Records	
Sedation usage	Duration of sedation (in Hours) and total dosage	Total duration of sedation after extubation measured in hours and total dosage	Numeric	Based on Hospital Records	
COMFORT scale	Patient's comfort during sedation post extubation	Patient's comfort measured in COMFORT behavioral scale	Categoric	COMFORT behavioural scale assessment	

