## CHAPTER II Literature Review

Pediatric patients undergoing cardiac surgery are at high risk of developing respiratory complications, particularly following extubation. Unsuccessful extubation can lead to respiratory failure, increasing the need for reintubation and further medical interventions. Extubation failure is defined as the necessity for reintubation within 72 hours after planned extubation. Several studies have reported that the incidence of extubation failure in pediatric post-cardiac surgery patients ranges from 9.7% to 17.6%, depending on factors such as cardiopulmonary bypass (CPB) duration, congenital heart disease severity, and high inotropic support requirements. One potential strategy to reduce this rate is the implementation of non-invasive ventilation (NIV) or high-flow nasal cannula (HFNC) as a transitional modality before initiating low-flow oxygen therapy. However, the effectiveness of these approaches remains controversial, particularly in high-risk post-cardiac surgery populations. Furthermore, at the RSCM Cardiac ICU, a modified form of NIV is still in use, which may not be ideal due to the potential for inadequate airflow delivery.

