### 4.3. Population and Sample

The study population consists of **pediatric patients undergoing post-cardiac surgery** and receiving care in the **CICU at RSUPN Cipto Mangunkusumo, Jakarta**. The study sample will be selected based on predefined **inclusion and exclusion criteria**, with the total sample size determined using an appropriate statistical estimation formula. The sample size estimation will be calculated using the following formula:

$$n1 = n2 = \left( \frac{Z\alpha\sqrt{2PQ} + Z\beta\sqrt{P1Q1 + P2Q2}}{P1 - P2} \right)^2$$

Description:

n1 = n2 = Sample size

Za = Standard deviation for Type I error = 5% = 1,96

Zb = Standard deviation for Type II error = 20% = 0,84

P1 – P2 = Minimum significant difference in proportion = 0,25

P2 = Extubation failure rate with HFNC based on literature is 17% or equivalent to 0,17.

Q2 = 1 – 0,17 = 0,83

P1 = P2 + 0,25 = 0,17 + 0,25 = 0,42

Q1 = 1 – P1 = 1 – 0,42 = 0,58

P = (P1 + P2)/2 = (0,42 + 0,17)/2 = 0,295

Q = 1 – P = 1 – 0,295 = 0,705

$$n1 = n2 = \left( \frac{1,96\sqrt{2x0,295x0,705} + 0,84\sqrt{0,42x0,58 + 0,17x0,83}}{0,42 - 0,17} \right)^2 = 51$$

Meanwhile, when estimating the sample size based on the outcome of reintubation rate reduction, the calculation is as follows

$$n1 = n2 = \left( \frac{Z\alpha\sqrt{2PQ} + Z\beta\sqrt{P1Q1 + P2Q2}}{P1 - P2} \right)^2$$

Description:

P1 (HFNC) = 0.37 (HFNC reintubation rate)

P2 (NIV) = 0.15 (NIV reintubation rate)

P1 - P2 = 0.25 (Difference to be detected)

Q1 = 1 - P1 = 1 - 0.37 = 0.63

Q2 = 1 - P2 = 1 - 0.15 = 0.88

P = (P1 + P2) / 2 = (0.37 + 0.17) / 2 = 0.245

Q = 1 - P = 1 - 0.245 = 0.755

$$n1 = n2 = \left( \frac{1,96\sqrt{2x0,245x0,755} + 0,84\sqrt{(0,37x0,63) + (0,12x0,88)}}{0,25} \right)^2$$

= 45.22 ~ 46 subjects

Similarly, when estimating the sample size based on the outcome of mortality reduction, the calculation is as follows:

$$n1 = n2 = \left( \frac{Z\alpha\sqrt{2PQ} + Z\beta\sqrt{P1Q1 + P2Q2}}{P1 - P2} \right)^2$$

Description:

P1 (HFNC) = 0.1 (Mortality rate with HFNC)

P2 (NIV) = 0.35 (Mortality rate with NIV)

P1 - P2 = 0.25 (The difference to be detected)

Q1 = 1 - P1 = 1 - 0.1 = 0.9

$$Q2 = 1 - P2 = 1 - 0,35 = 0,65$$

$$P = (P1 + P2) / 2 = (0,1 + 0,33) / 2 = 0,225$$

$$Q = 1 - P = 1 - 0,225 = 0,77$$

$$n1 = n2 = \left( \frac{1,96\sqrt{2 \times 0,225 \times 0,775} + 0,84\sqrt{(0,1 \times 0,9) + (0,35 \times 0,65)}}{0,25} \right)^2$$
$$= 42,54 \sim 43 \text{ subjek}$$

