#### 4.4. Inclusion and Exclusion Criteria

**Inclusion Criteria:**

- Patients under 18 years of age.
- Post-cardiac surgery patients in the CICU of RSUPN.
- Patients at high risk of extubation failure (e.g., young age, open sternotomy, mechanical ventilation >48 hours).
- Patients who pass the extubation readiness test and spontaneous breathing trial.

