#### **4.8. Data Analysis**

[figure not shown]
Data will be processed using statistical software and analyzed through univariate and multivariate analyses.

- Univariate analysis will be used to describe subject characteristics.
- Multivariate analysis using binary logistic regression will be performed to identify factors influencing extubation failure.

[figure not shown]

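### Table 1 records age only as below or above 12 months; a numeric age would serve the factor analysis better at no cost

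*Protocol*

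**What the plan says.** Protocol, Chapter III, Table 1 (Operational Definitions) makes age a categorical variable with two levels, "Patient age categorized as less than 12 months" and "Patient age categorized as more than 12 months". In the same table weight, the vasoactive-inotropic score and the blood gas values are numeric.

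Section 4.4 admits "Patients under 18 years of age" with no lower limit, and requires "Patients at high risk of extubation failure (e.g., young age, open sternotomy, mechanical ventilation >48 hours"), so young age is one listed example of raised risk, with no cut-off attached.

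Section 4.8 plans one multivariable model: "Multivariate analysis using binary logistic regression will be performed to identify factors influencing extubation failure". It does not name the covariates or say how they enter. The model serves Research Question 2 (Section 1.4) and the second specific objective (Section 1.5).

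Table 1 also has two levels for operation type, off-CPB and CPB. Both rows carry the same definition, "Surgery without the use of cardiopulmonary bypass". Nothing else in the protocol amends the age or the CPB entry.

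**The concern.** The eligible range runs from birth to just under 18 years. The split puts newborns with 11-month-olds, and 13-month-olds with 17-year-olds. The protocol itself singles out neonates in Chapter II as a group with repeated extubation failure, so differences within infancy are part of what the factor analysis would want to see. If the two-level variable is what goes into the model, any gradient inside each level is lost, and the age effect is estimated less precisely than the same children would allow.

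Two smaller defects sit beside this. The levels are strict inequalities on both sides, so exactly 12 months has no category. And the CPB definition contradicts its own label.

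At stake is the quality of the factor analysis, which will have few events to work with. The comparison of the randomised arms is not at stake.

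**Working it through.** **1. The plan's own figures, and whether age enters them.** Section 4.3 uses z values of 1.96 and 0.84, P1 = 0.42, P2 = 0.17 and P = 0.295:

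n = [(1.96·√(2·0.295·0.705) + 0.84·√(0.42·0.58 + 0.17·0.83)) / 0.25]² = 50.98, i.e. 51 per group.

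Adding 10% gives 102 + 10.2 = 112.2, hence 57 per group and 114 in all. The figures reproduce. Age appears nowhere in them, so recoding age changes nothing here.

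**2. Events available to the factor analysis.**
- Planning rates (Section 4.3): 57 × (0.17 + 0.42) = 33.6, about 34 failures.
- Literature range (Section 1.1): 114 × 0.097 = 11.1 and 114 × 0.176 = 20.1, about 11 to 20 failures.

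**3. Information kept by a two-way split.** Assume a covariate X (say log age) that is about normal with a linear effect on the log-odds scale. Cutting it at the quantile q keeps, approximately, the squared correlation between X and its indicator:

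kept = φ(z_q)² / [q(1 − q)]

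| Cut at quantile | Kept | Lost |
|---|---|---|
| 0.5 | 0.637 | 36% |
| 0.7 (or 0.3) | 0.576 | 42% |
| 0.8 | 0.490 | 51% |

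The quantile at which 12 months falls is not known from the protocol. The table therefore shows a range under an assumption and is not an estimate for this trial.

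**4. Degrees of freedom.** A two-level age variable uses one model parameter. Log age as a single continuous term also uses one. The change asks nothing more of the 11 to 34 events.

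**5. The boundary.** Label and definition agree in each age row (less than, more than), so a symbol lost in text conversion does not explain the gap. A child of exactly 12 months is eligible under Section 4.4 and has no level in Table 1. Purely for scale, if ages were spread evenly over the 216 months below 18 years, 114/216 ≈ 0.5 child would be in any one month of age. A trial weighted towards infants would have more at that age, but still few.

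**6. The CPB row.** Set side by side, the two operation-type rows have opposite labels and one shared sentence. The sentence fits the off-CPB label and contradicts the other.

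**The case against.** The strongest case on the other side has four parts.

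- *Section 4.8 names no covariates.* Table 1 is a list of definitions. The age levels might serve only the description of subjects, and coding for a model is often left to a statistical analysis plan. This stands as a caveat: that age enters the regression is an inference. It is a reasonable one, since Table 1 is the only list of defined variables and this is the only multivariable model. Table 1 does more than leave the matter open, because it fixes age as categorical where weight is numeric.
- *Infant versus older child is an interpretable split.* True, and the protocol does not contradict itself by using it. If risk changes mainly around the first birthday, the loss would be smaller than the range above.
- *Numeric weight is also recorded.* In children it tracks age closely. A reader might infer that the split leaves residual confounding by age in every other factor's estimate. The protocol does not support that: only factors related to age could be affected, and a model containing weight would absorb part of it.
- *The CPB row is a copying slip.* A reader might infer that the two levels cannot be told apart, or that a CPB coefficient would be meaningless. That holds only if the label is ignored, and the label makes the intended meaning clear. The protocol's remarks about bypass in Chapter II concern its duration, which is a different variable.

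**Conclusion.** The point holds as a minor improvement. Table 1 fixes age in a form that is coarser than it needs to be for the one planned factor analysis, and leaves exactly 12 months unassigned. The loss for the age effect is roughly 36% to 51%, given three assumptions: log age is about normal, its effect is linear, and 12 months lies between the median and the 80th percentile. It also presumes that age is a candidate in the regression.

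A reader might restate the range as losing over a third of the 114 children. That is not supported as a flat statement: the range concerns the age effect alone, and depends on an age distribution that the protocol does not give.

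The boundary gap and the CPB wording are close to clerical. The unadjusted arm comparison, the sample size, alpha and power are unaffected.

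**What to change.** In Table 1, define age as a numeric variable in months, in the same way as weight. In the factor analysis of Section 4.8, enter it as a single continuous term, for example log age (with a small offset if a newborn can be recorded as 0 months). If an age category is also tabulated, make it <12 versus >=12 months so that every eligible child has a level.

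As a wording correction only, redefine the CPB row as surgery performed with cardiopulmonary bypass.

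The cost is a change to a few table entries and one sentence of the analysis section. It needs age recorded in months, which the protocol does not mention explicitly but which checking the under-18 criterion makes a small step. No extra model parameter and no extra children are required. The change is best made before data are coded.

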### **Research Methodology:**

This study is a randomized controlled clinical trial involving two intervention groups: one receiving High Flow Nasal Cannula (HFNC) therapy using AirvoTM3 Nasal High Flow/HFNC System and the other receiving Non-Invasive Ventilation (NIV). The study population consists of pediatric patients admitted to the Cardiac Intensive Care Unit (CICU) at [name] National General Hospital (RSCM) following cardiac surgery. A total of 114 subjects will be enrolled, with 57 patients allocated to each group. Patients will be monitored for 24 hours post-extubation to evaluate the incidence of extubation failure and the associated risk factors. Reintubation will be performed in cases of respiratory failure or other complications requiring airway support.

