### **Expected Outcomes:**

The use of HFNC is expected to achieve an extubation success rate that is comparable to NIV, while offering a lower risk of complications and enhanced patient comfort. The findings of this study are anticipated to provide significant evidence regarding the differences between these two modalities in preventing extubation failure.

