## CHAPTER 1 Introduction

### 1.1. Background

Congenital heart disease (CHD) is a significant global health concern, with a prevalence of 0.8–1.2% of total live births. In developed countries, post-cardiac surgery mortality rates among pediatric patients tend to be low. However, data from Indonesia, particularly from [name] National General Hospital (RSCM), indicate a significant mortality rate. Over the past 3–5 years, the post-cardiac surgery mortality rate among pediatric patients at RSCM has been approximately 13.6%, primarily due to complications such as low cardiac output syndrome (LCOS), arrhythmias, multi-organ dysfunction, and extubation failure. The incidence of extubation failure in pediatric cardiac surgery patients ranges from 9.7% to 17.6%, often associated with airway, neurological, cardiac, diaphragmatic, and electrolyte-related factors. Patients experiencing repeated extubation failure have a higher risk of mortality compared to those who either do not experience it or fail extubation only once. Therefore, identifying effective solutions to mitigate the risk of extubation failure is of critical importance.

Non-invasive ventilation (NIV) and high-flow nasal cannula (HFNC) are commonly implemented in healthcare centers to reduce the incidence of extubation failure. However, the effectiveness of HFNC in minimizing extubation failure among high-risk pediatric cardiac surgery patients remains uncertain, particularly in Indonesia. At RSCM, the systematic and widespread use of HFNC in managing post-cardiac surgery pediatric patients requires further investigation to establish its efficacy. This study aims to address this gap by comparing extubation success rates between HFNC and NIV at RSCM.

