### 1.3. Research Problem Statement

Given the high incidence of extubation failure among pediatric post-cardiac surgery patients at RSCM, there is a pressing need to identify a more effective approach to prevent extubation failure. This study aims to answer the following research question: **Is HFNC as effective as NIV in preventing extubation failure in pediatric patients following cardiac surgery?**

---

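### Table 1 tests only reintubation within 72 h, so a child who dies unreintubated in that window scores as a successful extubation, and a change of modality leaves no trace in the outcome

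*Protocol*

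**What the plan says.** Table 1 (Chapter III) gives two mirror-image rows. Success is "Patient does not require reintubation within 72 hours after extubation"; failure is "Patient requires reintubation within 72 hours after extubation". The Literature Review uses the same test: "Extubation failure is defined as the necessity for reintubation within 72 hours after planned extubation".

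Death appears in Table 1 only in a separate row, as "Number of patient deaths during CICU hospitalization". That row covers the whole CICU stay and is not linked to the 72 h outcome.

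No row in Table 1 records a change from HFNC to NIV or the reverse. The only escalation in the readable text is in the Research Methodology summary: "Reintubation will be performed in cases of respiratory failure or other complications requiring airway support". The procedures for the two groups are in Images 4 and 5, which are not visible in the text reviewed.

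The outcome serves the question in section 1.3, "Is HFNC as effective as NIV in preventing extubation failure in pediatric patients following cardiac surgery", and the Expected Outcomes summary says that HFNC is "expected to achieve an extubation success rate that is comparable to NIV".

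**The concern.** Extubation success is meant to be a good result. Under Table 1, a child who dies 40 h after extubation without a tube being replaced meets the definition of success. Following the plan exactly therefore gives a wrong classification; this is more than a missing detail.

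A change of modality raises a different issue. A child who does badly on the assigned support, is moved to the other arm's device and avoids reintubation is a success for the assigned arm. That may be intended. But the comparator is itself a possible second support, so a reader of the result needs to know how often this happened. Without a variable for it, an apparent similarity or difference between the arms cannot be interpreted.

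The trial is small, so a few such children in one arm would be visible in the result.

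**Working it through.** **1. Classification under Table 1 as written**

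| Course within 72 h of extubation | Reintubated? | Table 1 result |
|---|---|---|
| Alive, on assigned support | No | Success |
| Reintubated | Yes | Failure |
| Dies without reintubation | No | Success |
| Moved to the other modality, alive | No | Success |

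The verb in the definition could be read as need rather than event, so that a dying child might be said to have needed a tube. But the category label for the success row is the absence of reintubation in 72 hours, which supports the event reading.

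**2. The plan's own sample size**

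Inputs from section 4.3: 1.96, 0.84, P1 = 0.42, P2 = 0.17 (HFNC), P = 0.295, Q = 0.705.

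n = [(1.96√(2 × 0.295 × 0.705) + 0.84√(0.42 × 0.58 + 0.17 × 0.83)) / 0.25]² = 50.98, so 51 per group. Allowing for 10% loss, 51/0.9 = 56.7, so 57. The plan's figures reproduce.

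One child is 1/57 = 1.75 percentage points of an arm.

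**3. Deaths without reintubation (assumed rates)**

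The documents give no 72 h death rate. Difference with death counted as failure = (reintubation + death in one arm) − (reintubation + death in the other). Start from 0.42 vs 0.17, with 51 per group analysed. Power = Φ[(|P1 − P2|√n − 1.96√(2PQ)) / √(P1Q1 + P2Q2)].

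| Deaths, arm at 0.42 | Deaths, arm at 0.17 | Difference (points) | Power |
|---|---|---|---|
| 0 | 0 | 25 | 0.800 |
| 3% | 3% | 25 | 0.777 |
| 5% | 0 | 30 | 0.913 |
| 0 | 5% | 20 | 0.583 |

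Five per cent of 57 is 2.85, about three children. Balanced deaths leave the difference alone; unbalanced deaths move it either way.

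**4. Change of modality (assumed rates)**

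Let h be the HFNC reintubation rate with no switching, and r the share of those failures that NIV support spares from reintubation. Observed HFNC rate = h(1 − r). The base rates are the plan's own, plus an equal-arms case. Cells show HFNC minus NIV in points, with power at 51 per group in brackets.

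| Base rates, HFNC vs NIV | r = 0 | 10% | 20% | 30% | 50% |
|---|---|---|---|---|---|
| 0.37 vs 0.12 (second calculation, as used in its formula) | +25.0 (0.846) | +21.3 (0.736) | +17.6 (0.593) | +13.9 (0.432) | +6.5 (0.147) |
| 0.17 vs 0.17 | 0 | −1.7 | −3.4 | −5.1 | −8.5 |
| 0.17 vs 0.42 (first calculation, taking 0.42 as the NIV rate) | −25.0 (0.800) | −26.7 (0.858) | −28.4 (0.905) | −30.1 (0.940) | −33.5 (0.982) |

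The second calculation states the NIV rate as 0.15 but puts 0.12 into the formula. With 0.15, the first row becomes +22.0, +18.3, +14.6, +10.9 and +3.5.

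Switching from NIV to HFNC works in mirror image. With 0.17 vs 0.42 and r = 20%, NIV falls to 0.42 × 0.8 = 0.336 and the gap shrinks from 25 to 16.6 points.

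So support that spares reintubation always lowers the observed failure rate of the arm switched from. Whether that narrows or widens the difference depends on the true rates, and the plan's two calculations put HFNC on opposite sides.

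**The case against.** **Reintubation by randomised arm, whatever support follows, is a legitimate treatment-policy outcome.** This stands. It compares starting with HFNC against starting with NIV, and on that reading a switched child is correctly a success. The protocol does not say that this is its target, but the choice is no error. The argument does not extend to death: a child who died is not a success under any reading of the question.

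**Switching is not documented.** This also stands. No readable text says that children move between devices, and Images 4 and 5 might allow it, bar it or count it as an event. A reader might infer that NIV rescue of HFNC failures is a working feature of the trial; the documents do not support that.

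**The direction is not fixed.** A reader might infer a bias toward the hoped-for finding of comparability. For HFNC-to-NIV switching that needs HFNC to be truly worse. With equal arms or HFNC better, it flatters HFNC instead. For deaths, the direction depends on the arm.

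**The data may be captured anyway.** Partly so. Section 4.7 says that clinical condition is recorded throughout the stay, and CICU deaths are an outcome. But no defined variable gives the time, direction and reason of a change of support.

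**This belongs in the SAP.** A supportive analysis could sit there. The outcome definition, however, is fixed in the protocol.

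**Conclusion.** The point holds in a limited form. Table 1 classifies a child who dies unreintubated within 72 h as a success, and that should be corrected. It also scores a child moved to the other modality as a success, with no Table 1 variable to show it; that should be made visible.

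No size or direction can be claimed. The switch shares and death rates above are assumptions that show a range. Section 1.1 gives a post-cardiac-surgery "mortality rate among pediatric patients at RSCM has been approximately 13.6" per cent, and a reader might be tempted to use this as the death rate. It refers to post-surgical mortality generally and is not a 72 h post-extubation rate. What can be said is that each reclassified child is worth 1.75 points in an arm of 57, and that a three-child imbalance in deaths would move the difference by about 5 points.

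**What to change.** 1. In Table 1, define failure as reintubation or death within 72 h of extubation, and success as alive and not reintubated at 72 h. Align the Literature Review definition.
2. Add a Table 1 variable for any change of assigned support: time, direction and reason.
3. Report by randomised arm a supportive sensitivity outcome of reintubation, death or change of modality within 72 h, with the three components shown separately.

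The cost is a few form fields and one extra analysis. Its weakness is that the switch component is decided by clinicians and so can reflect device preference. It should therefore inform interpretation and not act as a condition for the main conclusion. No change to patient care is proposed.

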### **Outcome of Study:**

The expected outcomes include a reduction in reintubation rates at 48 - 72 hours, 7 days, and 28 days post-extubation in the HFNC group compared to the NIV group. Additionally, this study aims to decrease mortality rates in the CICU and shorten the length of hospital stay for pediatric patients following cardiac surgery.

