### **Comparison of the Effectiveness of HFNC and NIV**

Studies comparing HFNC and NIV in pediatric post-cardiac surgery patients have yielded mixed results. Some research supports HFNC as a more comfortable and easier-to-implement modality, particularly due to its less invasive nasal cannula interface compared to the masks used in NIV. Furthermore, HFNC is considered more user-friendly in non-ICU settings. Conversely, NIV has been utilized for a longer duration in intensive care settings and is known for providing stable positive pressure, which helps prevent alveolar collapse and improves gas exchange in patients with compromised pulmonary function.

[figure not shown]
A study by Zhou et al. (2024) found that HFNC significantly reduced reintubation risk (RR = 0.36,  $P < 0.00001$ ) and shortened ICU stay duration (MD = -4.75,  $P = 0.04$ ). Similarly, research by Elmitwalli et al. (2024) reported that HFNC decreased reintubation rates (RR = 0.45,  $P < 0.01$ ), mortality (RR = 0.31,  $P < 0.01$ ), as well as length of hospital stay (-8.76 days,  $P < 0.01$ ) and ICU stay (-4.63 days,  $P = 0.04$ ). However, compared to conventional oxygen therapy, no significant differences were observed in reintubation rates. A study by Kuitunen (2023) concluded that there was insufficient evidence to establish a definitive difference in reintubation rates and other clinical outcomes between different non-invasive ventilation strategies, due to high bias risk and limited study numbers.

The debate continues regarding which modality is more effective in reducing extubation failure and mortality. HFNC provides benefits for patients with moderate-to-severe respiratory failure risk, whereas NIV may be more suitable for patients with severe pulmonary conditions. Further research is required to determine the optimal post-extubation strategy for pediatric post-cardiac surgery patients.

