## CHAPTER IV Research Methodology

### 4.1. 4.1. Study Design

This study employs a Randomized Controlled Trial (RCT) design to compare two intervention groups: patients receiving oxygen therapy using Non-Invasive Ventilation (NIV) and those receiving therapy with High Flow Nasal Cannula (HFNC) using AirvoTM3 Nasal High Flow/HFNC System. Patients will be monitored for the incidence of extubation failure and other clinical parameters throughout their hospitalization.

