#### **4.7. Data Collection Technique**

[figure not shown]
Data is collected through clinical observation and measurement of patients' respiratory parameters before and after therapy. A blood sample of 0.5–1.0 mL is taken one hour before and after therapy. Monitoring is conducted by a trained medical team, and data on extubation failure, vital parameters, and patients' clinical conditions are continuously recorded during hospitalization.

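### Reintubation is an outcome at 28 days post-extubation, but the readable protocol describes observation only in hospital, so later events can be missed and observed time may differ by arm

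*Protocol*

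**What the plan says.** Table 1 (Chapter III) defines the outcome as "Frequency of patients requiring reintubation at 72 hours, 7 days and 28 days" and gives clinical observation as its only source. In the same table, CICU and hospital stay come from hospital records. The Outcome of Study section sets the clock and the comparison: it expects a "reduction in reintubation rates at 48 - 72 hours, 7 days, and 28 days post-extubation in the HFNC group compared to the NIV group".

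The observation windows are described elsewhere:

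- Section 4.1: "Patients will be monitored for the incidence of extubation failure and other clinical parameters throughout their hospitalization".
- Section 4.7: data on extubation failure, vital parameters and "patients' clinical conditions are continuously recorded during hospitalization".
- The Research Methodology summary gives a shorter window: "Patients will be monitored for 24 hours post-extubation to evaluate the incidence of extubation failure".

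No readable section describes a visit, call or readmission check after discharge. The Outcome of Study section also aims at a shorter hospital stay. The Chapter II comparison of HFNC and NIV cites a systematic review in which hospital stay was 8.76 days shorter with HFNC.

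**The concern.** A frequency at a fixed horizon needs each child's status at that horizon. If observation ends at discharge, a child who leaves on day 12 has been observed for 12 of the 28 days, and a later readmission with reintubation goes unseen unless someone looks for it. The figure reported would be an in-hospital rate under a 28-day label.

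Equal loss in both arms would mainly understate the rate. Here the loss may be unequal, because length of stay is something the treatment is hoped to change. If HFNC children go home sooner, they are observed for less time. Any events missed for that reason favour HFNC, which is the direction the Outcome of Study section expects. Randomisation does not protect against this, since stay is determined after randomisation.

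**Working it through.** **The plan's own figure.** The protocol gives no 28-day rate to reproduce. Its governing sample size is for extubation failure, which Table 1 defines within 72 hours. With 0.42 vs 0.17 and z values 1.96 and 0.84, the formula in section 4.3 gives 50.98, i.e. 51 per group. Then 102 × 1.10 = 112.2, rounded to 113, which gives 57 per group and 114 in total. This reproduces and does not depend on events after 72 hours, unless children leave hospital within 72 hours.

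**Inputs for the illustration.**
- From the documents: horizon 28 days; stay difference 8.76 days (cited review); early rate 17% (section 4.3).
- Assumed: true day 3 to 28 risk r of 2%, 5% or 10%, equal in both arms; constant hazard that continues unchanged after discharge; discharge exponential from day 3; mean NIV discharge on day 15, 20 or 25 post-extubation and HFNC 8.76 days earlier; post-discharge events unseen and counted as none.

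**Formula.** With h = −ln(1 − r)/25 and m = 1/(mean discharge day − 3), the recorded late risk is h/(h + m) × (1 − exp(−25(h + m))).

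Example with r = 5% and mean discharge on day 15 (NIV) vs 6.24 (HFNC): h = 0.00205; m = 1/12 = 0.0833 and 1/3.24 = 0.3086. Recorded late risks are 2.1% and 0.7%.

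| Mean NIV discharge day | Discharged before day 28, NIV / HFNC | Recorded late risk at r = 5%, NIV / HFNC | Plus 17% early rate | 28-day RR |
|---|---|---|---|---|
| 15 | 88% / 100% | 2.1% / 0.7% | 19.1% / 17.7% | 0.93 |
| 20 | 77% / 95% | 2.6% / 1.6% | 19.6% / 18.6% | 0.95 |
| 25 | 68% / 85% | 3.0% / 2.3% | 20.0% / 19.3% | 0.97 |

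Carrying more decimals, or applying the late risk only to the 83% not reintubated early, moves these ratios by about 0.01. Over r = 2% to 10%, the spurious difference runs from 0.3 points (r = 2%, day 25) to 2.9 points (r = 10%, day 15).

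**Second model.** Take a fixed stay L in each arm, again 8.76 days apart, and let x be the late risk in points of all children. With h = −ln(1 − x/0.83)/25, the recorded 28-day risk is 0.17 + 0.83 × (1 − exp(−h(L − 3))). For L = 14, 20 or 28 days in the longer-stay arm, the spurious difference is about 0.7 points at x = 2, 1.7 to 1.8 at x = 5, and 3.4 to 3.6 at x = 10. With 57 per arm, the chance of a significant result in that direction is about 3% to 7% for late risks of 1 to 10 points, against a nominal 2.5%.

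**Sensitivity to post-discharge risk.** Both models keep the hazard unchanged after discharge, which is the unfavourable case. In the fixed-stay model with x = 5 and L = 20, if the hazard falls to a quarter after discharge, true 28-day risks are 20.83% and 19.52%, a real difference of 1.31 points. The recorded difference is 1.75 points, so only 1.75 − 1.31 = 0.44 points is spurious. With no hazard after discharge nothing is missed and the bias is zero.

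**The case against.** A reader might infer that children discharged early count as event-free, and that the arm discharged sooner will therefore look better with no true difference. The documents do not support that much. No section says how a child with unobserved day-28 status is classified; event-free is only the natural reading of a simple frequency. A handling rule could stand in the SAP, which is not at hand. The 10% allowance for loss to follow-up shows that incomplete follow-up was foreseen.

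Nor does the text say that recording stops at discharge. It describes in-hospital recording and is silent on anything later. The flowchart and group-procedure images are not shown and might contain a contact.

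The evidence on stay is also weaker than it looks. The review with the 8.76-day difference also reports fewer reintubations with HFNC (RR 0.45), so part of the shorter stay may result from that. Another review cited there found too little evidence of a difference between strategies. Finally, 28-day reintubation is in neither the specific nor the secondary objectives.

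All of this limits the wording and the size. The mismatch remains. A SAP can classify a discharged child but cannot recover an event that nobody recorded, and the 10% allowance adds patients without establishing anyone's day-28 status. If a hidden figure does contain a contact, sections 4.1 and 4.7 still need to agree with it.

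**Conclusion.** The point holds as a gap in ascertainment. A 28-day between-arm outcome is paired with observation described only in hospital, no day-28 check is described, and stay may differ by arm. The comparison can be biased in favour of the arm discharged sooner; it is not shown that it will be.

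The size is modest: at most about 0.3 to 3 points for late risks of 2% to 10% with exponential discharge (up to 3.6 points with fixed stays), against a design difference of 25 points. It depends on an assumed late risk, assumed stays and an unchanged hazard after discharge, none of which the documents supply.

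A reader looking only at days 3 to 28 might quote spurious relative risks of 0.31 to 0.75 (at r = 5%, 0.31, 0.60 and 0.75 for mean NIV discharge on day 15, 20 and 25). Those describe the late component alone. The outcome in Table 1, read as a cumulative frequency at 28 days, includes the first 72 hours, and on that scale the ratio is about 0.93 to 0.97 at a 5% late risk. The point is worth correcting, but it does not threaten the main 72-hour comparison.

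**What to change.** In Table 1 and section 4.7, state that day-28 reintubation status will be ascertained for every child discharged alive before day 28, by a readmission record check or one call to the family or the receiving hospital, and that a reintubation found this way counts. Bring section 4.1 and the 24-hour sentence in the Research Methodology summary into line with the horizons in Table 1.

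If that follow-up is not wanted, rename the outcome as in-hospital reintubation up to day 28 in the Outcome of Study section and in Table 1, and make no 28-day claim. The treatment of live discharge and death as competing events can then be set in the SAP.

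The cost is one check or call per child discharged early, or two wording changes and a slightly weaker claim. No extra patients are needed. The first option should be in place before children are discharged.
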